4.3 Participant Selection

Participant selection was done by the study sites. However, the Data Coordinating Center provided lists of children to prioritize based on gestational age. Additionally, the Data Coordinating Center create and reviewed reports of enrollment by site, sex and gestational age to ensure balanced enrollment between treatment groups.

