9.2 Definition of Analysis Variables

The following table defines each of the effectiveness and process analysis variables.

Variable	Type	Definition
Primary Outcome		
BSID-III scores	Continuous	
The unit of analysis is the child enrolled in the study. The three associated outcomes will be the mean scaled composite cognitive, language and motor BSID-III scores assessed and reported at 36 months of life (+/- 3 months). The cognitive score will be considered primary.
 
Raw scores will be summarized but not analyzed.
 
Analysis Population: ITT

Low BSID-III scores	Binary	
The unit of analysis is the child enrolled in the study. The three associate outcomes will be whether the child scored less than an 85 on each of the composite cognitive, language and motor BSID-III scaled composite scores assessed at 36 months of life (+/- 3 months).
 
Cognitive scores < 54 and motor scores < 45 will have missing associated binary outcomes.
 
Analysis Population: ITT

Secondary Outcome		
ASQ-3 scores	Continuous	
The unit of analysis is the child enrolled in the study. The 5 associated outcomes will be the scores of the components of the ASQ-3 assessment, including communication, gross motor, fine motor, problem solving and personal-social.
 
Analysis Population: ITT

Variable	Type	Definition
Low ASQ-3 scores	Binary	
The unit of analysis is the child enrolled in the study. The outcome will be whether the child scored 2 standard deviations less than the mean on each of the communication, gross motor, fine motor, problem solving and personal-social ASQ-3 scores assessed at 36 months of life (+/- 3 months). Established, published cut-offs using US standards will be used as there are no region specific cut-offs established for the study sites.
 
Analysis Population: ITT

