Mean (SD)												
Median (P25, P75)												
Minimum - Maximum												
Summed Language Scaled Score, N												
Mean (SD)												
Median (P25, P75)												
Minimum - Maximum												
Fine Motor Scaled Score, N												

Mean (SD)												
Median (P25, P75)												
Minimum - Maximum												
Gross Motor Scaled Score, N												
Mean (SD)												
Median (P25, P75)												
Minimum - Maximum												
Summed Motor Scaled Score, N												
Mean (SD)												
Median (P25, P75)												
Minimum - Maximum												
Composite Scores												
Cognitive Composite Score, N												
Mean (SD)												
Median (P25, P75)												
Minimum - Maximum												
Language Composite Score, N												
Mean (SD)												
Median (P25, P75)												
Minimum - Maximum												
Motor Composite Score, N												
Mean (SD)												
Median (P25, P75)												
Minimum - Maximum												
Low Composite Scores												
Cognitive Composite Score <85												
Language Composite Score <85												
Motor Composite Score <85												

Table 4: ASQ Outcome Descriptive Statistics

Table 5a: BSID-III Adjusted Mean Estimates

Variable	Adjusted ¹ Mean (95% CI)		
	Aspirin	Placebo	Difference
BSID III Composite Scores			
Cognitive Composite Score			
Language Composite Score			
Motor Composite Score			
BSID III Scaled Scores			
Cognitive Scaled Score			
Receptive Language Scaled Score			
Expressive Language Scaled Score			
Summed Language Scaled Score			
Fine Motor Scaled Score			
Gross Motor Scaled Score			
Summed Motor Scaled Score			

Table 5b: BSID-III Adjusted Risk Ratio Estimates

	Aspirin n (%)	Placebo n (%)	RR (95% CI)
BSID III Composite Scores			
Cognitive Composite Score <85			
Language Composite Score <85			
Motor Composite Score <85			

1. Mean estimates and 95% confidence intervals from a regression model adjusting for site, gender, breast feeding, stunting and family care indicators.

Table 6a: ASQ Adjusted Mean Estimates

Variable	Adjusted ¹ Mean (95% CI)		
	Aspirin	Placebo	Difference
ASQ Total Score			
Communication total score			
Gross motor total score			
Fine motor total score			
Problem solving total score			
Personal-social total score			

Table 6b: ASQ Adjusted Risk Ratio Estimates

	Aspirin n (%)	Placebo n (%)	RR (95% CI)
ASQ Scores Below Cut Off			
Communication total score < 27.93			
Gross motor total score < 30.68			
Fine motor total score < 35.39			

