Problem solving total score < 16.71			
Personal-social total score < 32.53			

1. Mean estimates and 95% confidence intervals from a regression model adjusting for site, gender, breast feeding, stunting and family care indicators.

Figure 1: Consort Diagram

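### Low ASQ-3 is scored with one raw cut-off per domain for every child aged 33 to 39 months, with no questionnaire form or reference age named and no age term in the models

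*Combined protocol and SAP*

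**What the plan says.** SAP 9.2 gives the binary definition for each of the five domains: "The outcome will be whether the child scored 2 standard deviations less than the mean", assessed at 36 months plus or minus 3. On the source of the limits it says: "Established, published cut-offs using US standards will be used as there are no region specific cut-offs established for the study sites". The reason given concerns region. Age and questionnaire form are not mentioned.

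The only numerical limits in either document are in the Table 6b shell (SAP section 14). The first row reads "Communication total score < 27.93". The limits for the other four domains are 30.68 (gross motor), 35.39 (fine motor), 16.71 (problem solving) and 32.53 (personal-social).

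None carries an age band. The same section allows the shells to be updated without an SAP amendment.

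Age at assessment is absent from the candidate covariates (SAP 7.2), from the model description for ASQ-3 and binary outcomes, which names site (SAP 9.5), and from the footnote listing the adjustment variables for the adjusted tables. SAP 4.3 has the coordinating centre review "reports of enrollment by site, sex and gestational age to ensure balanced enrollment between treatment groups"; testing age is not among those factors. Protocol 3.3 states a preference for children of 36 months or more, on the ground that differences in age may influence the test.

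**The concern.** A limit set at mean minus 2 SD on a raw developmental total holds for the age at which that mean and SD were taken. The BSID-III composites are analysed on a scale assumed to have mean 100 and SD 15, whereas the ASQ-3 outcomes are raw domain totals. If the expected ASQ-3 total rises over the six-month window and all children are judged against a mid-window value, the limit is too strict for the youngest and too lenient for the oldest. Whether a child counts as low then depends partly on when the child was tested.

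What is at stake is the classification of individual children and the comparability of low-score percentages across sites or regions with different testing ages. Such differences are plausible: sites start at different times, and children close to ageing out are given priority (protocol 3.3 and 3.4).

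**Working it through.** **What can be reproduced.** The documents give no ASQ-3 mean, SD, form or age slope, so the Table 6b values cannot be re-derived. The one design figure that can be checked is the BSID-III sample size: 2 × 15² × (1.645 + 0.842)² / (4 − 1)² ≈ 309.1, hence 310 per arm and 620 in total, as stated. This point does not affect it.

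**Inputs from the documents.** Protocol Table 1 counts available children by month of age on 1 July 2021: 531 (33 months), 544, 434, 399, 419, 444 and 531 (39 months), 3,302 in all. The mean is 35.9 months and the SD 2.08. The two end months hold 1,062 / 3,302 = 32%. I use this pool as a stand-in for the ages at testing, which are not known.

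**Assumptions.** Scores are normal with domain SD 12. The fixed value is mean minus 2 SD at 36 months. The mean rises by d = 1, 2 or 3 points per 3 months on one common raw scale.

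**Formula.** P(low at age a) = Φ(−2 − (d/12) × (a − 36)/3). The intended share is Φ(−2) = 2.28%.

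| d (points per 3 months) | 33 months | 39 months | Ratio | Overall, weighted by Table 1 ages |
|---|---|---|---|---|
| 0 | 2.28% | 2.28% | 1.0 | 2.28% |
| 1 | 2.76% | 1.86% | 1.5 | 2.30% |
| 2 | 3.34% | 1.51% | 2.2 | 2.37% |
| 3 | 4.01% | 1.22% | 3.3 | 2.47% |

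Example, d = 3: Φ(−2 + 0.25) = Φ(−1.75) = 4.01% and Φ(−2.25) = 1.22%; 4.01 / 1.22 = 3.3.

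With the slope written in SD per month, 0.02, 0.05 and 0.10 give ratios of 1.3, 2.0 and 4.2.

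**Effect on the comparison of arms**, same assumptions, d = 1 to 3:

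- *Chance age imbalance.* The SE of the difference in mean age is 2.08 × √(2/310) = 0.17 month. If one arm is 0.25 month younger (about 1.5 SE), the spurious risk ratio is Σ nₐ P(a − 0.25) / Σ nₐ P(a) = 1.02 to 1.05.
- *Dilution.* For a true shift of 0.2 SD, the risk ratio is Φ(−1.8) / Φ(−2) = 1.58 with age-correct limits and 1.58 to 1.56 with the fixed limit. For 0.1 SD it is 1.26 against 1.26 to 1.25.

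**Effect on site percentages.** Applying the same formula to each site's own Table 1 counts, the lowest and highest expected shares are 2.25% (Zambia, mean age 36.3) and 2.34% (Pakistan, mean age 35.6) for d = 1, and 2.30% and 2.58% for d = 3. With that pool the spread is modest. It would widen if a site's actual testing ages clustered towards one end of the window.

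**The case against.** The case for leaving the plan alone has several parts.

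- *The premise is not documented.* No ASQ-3 norms are given, so it is not shown that they change between 33 and 39 months. This stands, and the point is conditional for that reason.
- *The values may be those for 36 months.* SAP 9.2 refers to assessment at 36 months plus or minus 3, its text governs, and the shell can be updated. This reading is possible, but the documents do not state it. Because the shell can change without amendment and 9.2 gives no age rule, the definition should be settled in 9.2.
- *The direction depends on how the questionnaire was given.* The calculation describes one form used for everyone. If several forms were used, totals come from different item sets, and the pattern of too strict for the young and too lenient for the old does not follow. If only one form was used, matching the cut-off to the form changes nothing, and the age covariate does the work. Both parts are right, which is why the fix needs both elements and must begin by naming the form(s).
- *The arms are protected.* They derive from 1:1 randomisation, sites are masked, the Table 1 shell counts ASQ-3 assessments within the required age by arm, and Table 3 summarises age at BSID-III examination by arm. No mechanism for different testing ages by arm is shown. This stands: a reader might infer a diluted or spurious treatment effect, but under the stated assumptions both are small.
- *The outcome is exploratory.* SAP 7.5 says so, and the BSID-III cognitive endpoint is untouched. This limits the weight of the point without answering it.

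**Conclusion.** The gap is real and limited. The SAP states a 2-SD definition and implements it with one raw value per domain across a six-month window, without saying which form or age the values come from and without an age term in any ASQ-3 model. If norms differ across the window, the limits cannot represent 2 SD below the mean at every child's age. The 1.5- to 3.3-fold difference between the ends of the window rests on assumed values for the SD and slope, a mid-window cut-off, normal scores and one common form. With no slope the ratio is 1.0. The overall percentage and the arm risk ratio change little, so the consequence lies in individual classification and in site or regional percentages.

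Three stronger readings are not supported:

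- That low ASQ-3 definitely does not mean 2 SD below the mean at the child's age. The documents contain no norms that would show it.
- That the printed values are wrong because problem solving (16.71) is less than half of fine motor (35.39). Nothing in the documents says the domain limits should be similar.
- That the analysis flag conflicts with the 2-SD referral rule in protocol 2.4.10. No document says the sites use different limits from Table 6b.

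**What to change.** In SAP 9.2 and Table 6b:

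- name the ASQ-3 form or forms used and the age interval of each;
- define low as below the published cut-off for the form that the child completed;
- list the cut-offs by form and domain, checked against the published source.

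In SAP 9.5 and Tables 6a and 6b, add age at assessment as a covariate, and form as well if more than one was used. Add a summary of ASQ-3 testing age by arm. Make these changes before data lock.

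The cost is a lookup in the analysis program, one extra model term (two if several forms were used) and a revised shell. No new data collection is needed: the existing shells already call for age at the BSID-III examination and for whether the ASQ-3 fell within the required age.
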